7.0 ADVERSE EVENTS

This study will be conducted in compliance with the Data Safety Monitoring Plan (DSMP) of the Robert H. Lurie Comprehensive Cancer Center of Northwestern University (please refer to Appendices for additional information). The level of risk attributed to this study requires High Intensity Monitoring, as outlined in the DSMP. In addition, the study will abide by all safety reporting regulations, as set forth in the Code of Federal Regulations.

7.1 Adverse Event Monitoring

Adverse event data collection and reporting, which are required as part of every clinical trial, are done to ensure the safety of subjects enrolled in the studies as well as those who will enroll in future studies using similar agents. Adverse events are reported in a routine manner at scheduled times during a trial (see Section 5 for time points). In addition, certain adverse events must be reported in an expedited manner to allow for optimal monitoring and patient safety and care.

All patients experiencing an adverse event, regardless of its relationship to study drug, will be followed until:

- the adverse event resolves or the symptoms or signs that constitute the adverse event return to baseline;
- any abnormal laboratory values have returned to baseline;
- there is a satisfactory explanation other than the study drug for the changes

NU Study Number: NU 16B07
Other Study Number: CA 209-782

- observed; or
- death

7.2 Definitions & Descriptions

7.2.1 Adverse Event

An adverse event (AE) is any untoward medical occurrence in a patient receiving study treatment and which does not necessarily have a causal relationship with this treatment. An AE can therefore be any unfavorable and unintended sign (including an abnormal laboratory finding), symptom, or disease temporally associated with the use of an experimental intervention, whether or not related to the intervention.

Recording of AEs should be done in a concise manner using standard, acceptable medical terms. In general, AEs are not procedures or measurements, but should reflect the reason for the procedure or the diagnosis based on the abnormal measurement. Preexisting conditions that worsen in severity or frequency during the study should also be recorded (a preexisting condition that does not worsen is not an AE). Further, a procedure or surgery is not an AE; rather, the event leading to the procedure or surgery is considered an AE.

If a specific medical diagnosis has been made, that diagnosis or syndrome should be recorded as the AE whenever possible. However, a complete description of the signs, symptoms and investigations which led to the diagnosis should be provided. For example, if clinically significant elevations of liver function tests are known to be secondary to hepatitis, "hepatitis" and not "elevated liver function tests" should be recorded. If the cause is not known, the abnormal test or finding should be recorded as an AE, using appropriate medical terminology (e.g/ thrombocytopenia, peripheral edema, QT prolongation).

7.2.2 Severity of AEs

All adverse events will be graded according to the NCI Common Terminology Criteria for Adverse Events (CTCAE) version 4.03. The CTCAE v4.03 is available at <http://ctep.cancer.gov/reporting/ctc.html>

If no CTCAE grading is available, the severity of an AE is graded as follows:

- Mild (grade 1): the event causes discomfort without disruption of normal daily activities.
- Moderate (grade 2): the event causes discomfort that affects normal daily activities.
- Severe (grade 3): the event makes the patient unable to perform normal daily activities or significantly affects his/her clinical status.
- Life-threatening (grade 4): the patient was at risk of death at the time of the event.
- Fatal (grade 5): the event caused death.

7.2.3 Serious Adverse Events (SAEs)

All SAEs, regardless of attribution, occurring from time of signed informed consent, through 12 weeks after the last administration of study drug, must be reported upon discovery or occurrence (see section 7.4.3.4 for reporting details). An SAE is defined in regulatory terminology as any untoward medical occurrence that:

- **Results in death.**

If death results from (progression of) the disease, the disease should be reported as event (SAE) itself.

NU Study Number: NU 16B07
Other Study Number: CA 209-782

- **Is *life-threatening*.**
The patient was at risk of death at the time of the event; it does not refer to an event that hypothetically might have caused death if it were more severe.
- **Requires *in-patient hospitalization or prolongation of existing hospitalization for ≥ 24 hours*.**
- **Results in *persistent or significant disability or incapacity*.**
- **Is a *congenital anomaly/birth defect*.**
- Is associated with an overdose.
For purposes of this trial, an overdose will be defined as any dose exceeding the prescribed dose for nivolumab or ipilimumab by 20% over the prescribed dose. No specific information is available on the treatment of overdose of nivolumab or ipilimumab. In the event of overdose, nivolumab should be discontinued and the subject should be observed closely for signs of toxicity. Appropriate supportive treatment should be provided if clinically indicated. If an adverse event(s) is associated with ("results from") the overdose of a BMS product, the adverse event(s) is reported as a serious adverse event, even if no other seriousness criteria are met.
If a dose of BMS's product meeting the protocol definition of overdose is taken without any associated clinical symptoms or abnormal laboratory results, the overdose is reported as a non-serious Event of Clinical Interest (ECI), using the terminology "accidental or intentional overdose without adverse effect."
- All reports of overdose with and without an adverse event must be reported within 24 hours to the Sponsor and within 2 working days hours to BMS Global Safety.
- **Is an *important medical event*.**

Any event that does not meet the above criteria, but that in the judgment of the investigator jeopardizes the patient, may be considered for reporting as a serious adverse event. The event may require medical or surgical intervention to prevent one of the outcomes listed in the definition of "Serious Adverse Event".

For example: allergic bronchospasm requiring intensive treatment in an emergency room or at home; convulsions that may not result in hospitalization; development of drug abuse or drug dependency.

Progression of the cancer under study is not considered an adverse event unless it results in hospitalization or death.

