4.3.1 Dose delays: Ipilimumab and/or nivolumab

There will be no dose modifications allowed for management of toxicities.

Should the treating physician decide to delay treatment given suspicion for a drug-related side effect, the side effect should be attributed to one study drug to the best of the physician's ability. Either ipilimumab or nivolumab should be delayed based on this attribution, or both if a definite attribution is not possible. Both drugs can be held for a maximum of 56 days.

Ipilimumab and/or nivolumab administration should be delayed for the following until resolution to \leq Grade 1:

- Any Grade \geq 2 non-skin, drug-related adverse event, with the following exceptions:
 - Grade 2 drug-related fatigue or laboratory abnormalities do not require a treatment delay
 - Any Grade 3 skin, drug-related adverse event
 - Any Grade 3 drug-related laboratory abnormality, with the following exceptions for lymphopenia, leukopenia, AST, ALT, or total bilirubin:
 - Grade 3 lymphopenia or leukopenia does not require dose delay
 - If a subject has a baseline AST, ALT or total bilirubin that is within normal limits, delay dosing for drug-related Grade \geq 2 toxicity
 - If a subject has baseline AST, ALT, or total bilirubin within the Grade 1 toxicity range, delay dosing for drug-related Grade \geq 3 toxicity
- Any adverse event, laboratory abnormality, or intercurrent illness which, in the judgment of the investigator, warrants delaying the dose of study medication.

Immunotherapy agents such as nivolumab and ipilimumab are associated with AEs that can differ in severity and duration compared to other therapeutic classes of medications. Early recognition and management of AEs associated with nivolumab can mitigate severe toxicity. Corticosteroids are the primary therapy for drug-related AEs. Management algorithms have been developed to assist investigators in assessing and managing nivolumab associated AEs, which can be found in Appendix D of this protocol. The guidance provided in these algorithms should not replace the Investigator's medical judgment.

NU Study Number: NU 16B07
Other Study Number: CA 209-782

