4.3.2 Treatment discontinuation: Ipilimumab and/or nivolumab

Should the treating physician decide to discontinue treatment given suspicion for a drug related side effect, the side effect (adverse event) should be attributed to one study drug to the best of the physician's ability. Either ipilimumab or nivolumab should be discontinued based on this attribution, or both if definite attribution is not possible.

Ipilimumab and/or nivolumab should be discontinued permanently for the following:

- Any Grade 2 drug-related uveitis, eye pain, or blurred vision that does not respond to topical therapy and does not improve to Grade 1 severity within the re-treatment period OR requires systemic treatment
- Any Grade 3 non-skin, drug-related adverse event lasting > 7 days, with the following exceptions for laboratory abnormalities, drug-related uveitis, pneumonitis, bronchospasm, hypersensitivity reactions, infusion reactions, and endocrinopathies:
 - Grade 3 drug-related uveitis, pneumonitis, bronchospasm, hypersensitivity reaction, or infusion reaction of any duration requires discontinuation
 - Grade 3 drug endocrinopathies adequately controlled with only physiologic hormone replacement do not require discontinuation
 - Grade 3 drug-related laboratory abnormalities do not require treatment discontinuation except:
 - Grade 3 drug-related thrombocytopenia > 7 days or associated with bleeding (aside from minor bleeds \leq Grade 1) requires discontinuation
 - Any drug-related liver function test (LFT) abnormality that meets the following criteria require discontinuation:
 - AST or ALT $>$ 5-10 x ULN for > 2 weeks
 - AST or ALT $>$ 10 xUL
 - Total bilirubin $>$ 5 x ULN
 - Concurrent AST or ALT $>$ 3 xULN and total bilirubin $>$ 2 x ULN
- Any Grade 4 drug-related adverse event or laboratory abnormality, except for the following events which do not require discontinuation:
 - Grade 4 neutropenia $<$ 7 days
 - Grade 4 lymphopenia or leukopenia
 - Isolated Grade 4 amylase or lipase abnormalities that are not associated with symptoms or clinical manifestations of pancreatitis. PI and Data Monitoring Committee (DMC) should be consulted for Grade 4 amylase or lipase abnormalities.
 - Isolated Grade 4 electrolyte imbalances/abnormalities that are not associated with clinical sequelae and are corrected with supplementation/appropriate management within 72 hours of their onset

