4.8 Removal of Subjects from Study Treatment and/or Study as a Whole

Patients can be taken off the study treatment and/or study as a whole at any time at their own request, or they may be withdrawn at the discretion of the investigator for safety, behavioral or administrative reasons. The reason(s) for discontinuation must be clearly documented on the appropriate eCRF and may include:

- Patient voluntarily withdraws from treatment (follow-up permitted)
- Patient withdraws consent (no follow-up permitted)
- Patient is unable to comply with protocol requirements (follow-up permitted)
- Patient demonstrates disease progression (per parameters above, follow-up permitted)
- Patient experiences unacceptable toxicity
- Treating physician determines that continuation on the study would not be in the patient's best interest
- Patient becomes pregnant
- Patient develops a second malignancy that requires treatment which would interfere with this study
- Patient becomes lost to follow-up (LTF)

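### The overdose rule in Section 7.2.3 covers both drugs but discontinues only nivolumab, so a symptom-free ipilimumab overdose has no clear written action on ipilimumab

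*Combined protocol and SAP*

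**What the plan says.** Section 7.2.3 defines an overdose as "any dose exceeding the prescribed dose for nivolumab or ipilimumab by 20% over the prescribed dose". It adds that there is no specific information on treating an overdose of either drug, and then gives the instruction: "In the event of overdose, nivolumab should be discontinued and the subject should be observed closely for signs of toxicity". Supportive treatment is to follow if clinically indicated.

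An overdose with an associated adverse event is reported as serious. One without clinical symptoms or abnormal laboratory results is a non-serious event of clinical interest. Reporting covers both cases: "All reports of overdose with and without an adverse event must be reported within 24 hours to the Sponsor".

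The other rules on holding or stopping treatment name both drugs:

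- Section 4.3.1 opens its list of delay criteria with "Ipilimumab and/or nivolumab administration should be delayed for the following until resolution to" Grade 1 or lower.
- Section 4.3.2 opens its list with "Ipilimumab and/or nivolumab should be discontinued permanently for the following". Its attribution rule applies when the physician decides to stop treatment "given suspicion for a drug related side effect, the side effect (adverse event) should be attributed to one study drug", or both drugs if attribution is uncertain.
- Section 4.8 lets patients be taken off at their own request, or "they may be withdrawn at the discretion of the investigator for safety, behavioral or administrative reasons".

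The Grade 2 row of the infusion-reaction table in Section 4.3.3 names both drugs when it stops the infusion and when it sets premedication. If symptoms recur, it withholds only nivolumab for the rest of that visit.

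**The concern.** The definition covers two drugs and the action covers one. Staff who follow the overdose sentence after an ipilimumab overdose are told to stop nivolumab and are told nothing about ipilimumab. Section 11.6 requires the study to be run exactly as written except in an emergency, so the wording matters.

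The sentence also does not say whether discontinued means the current infusion or all later doses. Section 4.3.2 adds the word permanently when it means that.

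Ipilimumab is the drug whose dose is worked out from body weight at each infusion (Section 4.2.2), while nivolumab is a flat dose (Section 4.2.1). It is reasonable to expect dose-calculation errors to arise with ipilimumab, but that is an inference. The documents give no error rate.

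At stake is a clear default for the next ipilimumab dose.

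**Working it through.** This is mainly a comparison of text. The arithmetic only sets the thresholds and the schedule.

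**Thresholds.** Prescribed doses are from Sections 4.2.1 and 4.2.2, and the 20% is from Section 7.2.3. Threshold = prescribed dose × 1.20.

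- Ipilimumab: 1 mg/kg × 1.20 = 1.2 mg/kg. At an assumed 80 kg (the approximate median weight that Section 1.3.2 gives for nivolumab trials), this is 96 mg.
- Nivolumab: 240 mg × 1.20 = 288 mg, and 480 mg × 1.20 = 576 mg.

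**Which rule reaches the overdosed drug?**

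| Situation | Drug that 7.2.3 discontinues | Other rule reaching the overdosed drug |
|---|---|---|
| Nivolumab overdose | Nivolumab | Not needed |
| Ipilimumab overdose with a suspected drug-related event | Nivolumab | 4.3.1 and 4.3.2, according to attribution and severity |
| Ipilimumab overdose without symptoms or abnormal laboratory results | Nivolumab | None clearly; general discretion in 4.8 |

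The third row is the gap. Section 4.3.1 is triggered by an adverse event, laboratory abnormality or intercurrent illness. Section 4.3.2 is triggered by a suspected side effect and lists no overdose criterion. One could argue that an overdose is itself an untoward occurrence under Section 7.2.1, but Section 7.2.3 reports the symptom-free case as an overdose without adverse effect. Unless the investigator acts, the six-weekly ipilimumab schedule in Section 4.2.2 continues.

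**Can the nivolumab stop act on the day itself?** One cycle is 84 days. Ipilimumab every 42 days falls on days 1 and 43 of each cycle. Nivolumab 480 mg every 28 days from Cycle 2 day 29 falls on days 29 and 57 of Cycle 2, then on days 1, 29 and 57 of each later cycle. Day 43 from Cycle 2 onward is therefore an ipilimumab-only day, first on study day 84 + 43 = 127. This agrees with the treatment days 1, 29, 43 and 57 in footnotes 4 and 5 of Section 5.0. On shared days nivolumab is given first. If the roughly 30-minute gap is counted from the end of its infusion, it has finished before ipilimumab starts. Read as a same-day stop, the instruction then normally has nothing to act on when ipilimumab is overdosed.

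**Grade 2 row of Section 4.3.3.** The infusion is restarted only once symptoms resolve. A recurrence after restart therefore fits the Grade 3 description in the same table, which includes symptoms returning after initial improvement. The Grade 3 row names both drugs, and Section 4.3.2 says that a Grade 3 drug-related "hypersensitivity reaction, or infusion reaction of any duration requires discontinuation". What remains is a recurrence sentence that names one drug and does not point to the Grade 3 row.

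**The case against.** The strongest case on the other side has four parts.

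1. **A symptomatic overdose is already handled.** Sections 4.3.1 and 4.3.2 name both drugs, and 4.3.1 also permits delay for any adverse event on the investigator's judgment. This stands. It narrows the gap to the symptom-free overdose.

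2. **Stopping nivolumab after an ipilimumab overdose may be sensible.** Section 1.2.4 says the combination causes similar types of adverse events to either agent alone, in some cases more often. Holding the partner drug during observation is a plausible precaution. This stands too. A reader might infer that the sentence tells staff to do something wrong, but the documents do not support that. The defect is that ipilimumab is left out, and a correction should keep the option to hold nivolumab.

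3. **A recurrent ipilimumab reaction is not left without instruction.** A reader might infer from the Grade 2 row that it is. However, the row's first step stops whichever infusion is running, the Grade 3 row and 4.3.2 cover recurrence after improvement, and the table may be adapted to local standards. Only a wording mismatch is left.

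4. **A small excess is unlikely to matter.** The threshold of 1.2 mg/kg is 1.2 / 3.0 = 40% of the 3 mg/kg dose that Section 1.2.3 describes, given every 3 weeks for up to four treatments. Observation and the 24-hour report apply whichever drug is involved. This stands for a small, symptom-free excess. It does not speak to a larger dosing error, for which the rule is also meant.

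**Conclusion.** The point holds as a minor correction to a safety instruction. Of the three situations set out above, one has no clear written action on the overdosed drug: an ipilimumab overdose without symptoms or laboratory abnormality. In the symptomatic case the overdose sentence still omits ipilimumab, but other sections supply the action.

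The number of patients affected cannot be estimated. The documents give no rate for overdose or for recurring infusion reactions, and Section 4.3.3 calls infusion reactions unlikely. With 29 patients, few would be expected.

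A reader might infer a threat to the trial's conclusions. There is none: the definition of PFS, the rules at 15 and 29 patients, the power and the type I error do not depend on this wording. No harm from a small excess is claimed.

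The gap in the overdose sentence does not depend on what discontinued means there. The remark about same-day stopping also assumes that the 30-minute gap runs from the end of the nivolumab infusion.

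**What to change.** In Section 7.2.3, replace the overdose instruction with: *In the event of overdose, the overdosed drug should be discontinued (any ongoing infusion stopped and further doses of that drug held pending investigator review), and the other study drug may also be held at the investigator's judgment.* This names the right drug, settles what discontinued means, and keeps the option of holding the partner drug. Observation, supportive care and reporting stay as they are.

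As a minor conforming edit in the Grade 2 row of Section 4.3.3, say that on recurrence neither nivolumab nor ipilimumab is given again at that visit, and refer to the Grade 3 row for recurrence after improvement.

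The cost is two sentences in an amendment, with no added procedures, staff or patients.

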7.2.4 Unanticipated Problems Involving Risks to Subject or Others (UPIRSO)

A UPIRSO is a type of SAE that includes events that meet ALL of the following criteria:

- Is *unanticipated* in terms of nature, severity, or frequency
- Places the research subject or others at a different or *greater risk of harm*
- Is deemed to be *at least possibly related* to participation in the study.

7.3 Reporting of pregnancy and lactation

Although pregnancy and lactation are not considered adverse events, it is the responsibility of investigators or their designees to report any pregnancy or lactation in a subject (spontaneously reported to them), including the pregnancy of a male subject's female partner that occurs during the trial or within 120 days of completing the trial completing the trial, or 30 days following cessation of treatment if the subject initiates new anticancer therapy, whichever is earlier. All subjects and female partners of male subjects who become pregnant must be followed to the completion/termination of the pregnancy. Pregnancy outcomes of spontaneous abortion, missed abortion, benign hydatidiform mole, blighted ovum, fetal death, intrauterine death, miscarriage and stillbirth

NU Study Number: NU 16B07
Other Study Number: CA 209-782

must be reported as serious events (Important Medical Events). If the pregnancy continues to term, the outcome (health of infant) must also be reported.

7.4 Adverse Event Reporting

7.4.1 Routine Reporting

All routine adverse events, such as those that are expected, or are unlikely or definitely not related to study participation, are to be reported on the appropriate eCRF according to the time intervals noted in the appendices. Routine AEs will be reviewed by the Data Monitoring Committee (DMC) according to the study's phase and risk level, as outlined in the DSMP.

7.4.2 Determining if Expedited Reporting is Required

This includes all events that occur within 30 days of the last dose of protocol treatment. Any event that occurs more than 30 days after the last dose of treatment and is attributed (possibly, probably, or definitely) to the agent(s) must also be reported accordingly.

- 1) Identify the type of adverse event using the NCI CTCAE v 4.03.
- 2) Grade the adverse event using the NCI CTCAE v 4.03.
- 3) Determine whether the adverse event is related to the protocol therapy.

Attribution categories are as follows:

- Definite: AE is clearly related to the study treatment.
- Probable: AE is likely related to the study treatment.
- Possible: AE may be related to the study treatment.
- Unlikely: AE not likely to be related to the study treatment.
- Unrelated: AE is clearly NOT related to the study treatment.

- 4) Determine the prior experience of the adverse event.

Expected events are those that have been previously identified as resulting from administration of the agent. An adverse event is considered unexpected, for expedited reporting purposes only, when either the type of event or the severity of the event is not listed in:

- the current protocol
- the drug package insert
- the current Investigator's Brochure

